Group 4 (N=8-10)	ChAdOx1-HBV 2.5 x 10  vp + nivolumab 0.3 mg/kg	MVA 1 x 10  pfu + nivolumab 0.3 mg/kg														
Study Procedures and Frequency:	
The safety, tolerability and immunologic assessments to be performed are:
 
 
• Haematology (full blood count, haemoglobin, haematocrit, erythrocytes, mean cell volume, mean corpuscular haemoglobin, mean corpuscular haemoglobin concentration, leukocytes, neutrophils, lymphocytes, monocytes, eosinophils, basophils, fibrinogen, prothrombin time and INR, and platelets) will be analysed at screening, pre-vaccination on Days 0 and 28, on Days 7 and 35, and on Months 3, 6 and 9
 
• Biochemistry (sodium, potassium, urea nitrogen, creatinine and albumin) will be analysed at screening, pre-vaccination on Days 0 and 28, on Days 7 and 35, and on Months 3, 6 and 9
 
• Liver function tests (alkaline phosphatase, gamma-glutamyl transpeptidase, ALT, AST and direct bilirubin) will be analysed at screening, pre-vaccination on Days 0 and 28, on Days 7 and 35, and on Months 3, 6 and 9
 
• HBV disease markers in serum will be analysed at screening, pre-vaccination on Days 0 and 28, on Days 7 and 35, and on Months 3 (pre-vaccination for UK participants having the MVA-HBV boost only), 6 and 9
 
• A full physical examination will be performed at screening, pre-vaccination on Days 0 and 28 and Month 3 (for UK participants having the MVA-HBV boost only) and on Month 9. A symptom-directed physical examination will be performed on Days 7 and 35, and on Months 3 and 6
 
• Vital signs will be performed at screening, pre-vaccination and post-vaccination Days 0 and 28, on Days 7 and 35, and on Months 3 (pre-vaccination for UK participants having the MVA-HBV boost only), 6 and 9
 
• Local and systemic reactogenicity (pain, induration, warmth, erythema at the vaccination site plus feverishness, chills, myalgia, fatigue, headache, nausea, arthralgia, malaise) will be captured pre-vaccination and post-vaccination on Days 0 and 28 and
 
															

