### ***3.1.3 Stopping Criteria/Holding Criteria***

There will be a review of the study data by the DMC when there is a reasonable possibility that the investigational vaccine caused any of the SAEs or severe adverse events listed below, based on the assessment of the Investigator, in one or more participants at any dose. Vaccinations will be put on hold pending this review:

- Death related to study vaccine
- Life-threatening adverse event or life-threatening suspected reaction
- Serious suspected adverse reaction
- Suspected unexpected serious adverse reaction (SUSAR)
- Acute allergic reaction or anaphylactic shock following the administration of vaccine investigational product
- Anaphylaxis or bronchospasm, indicative of an immediate hypersensitivity reaction to study vaccine
- If any participant has any of the following during the study:
  - Alanine aminotransferase (ALT) or aspartate aminotransferase (AST) >3 x upper limit of normal (ULN) and total bilirubin >2 x ULN or International Normalised Ratio (INR) >1.5
  - ALT or AST >3 x ULN with the appearance of fatigue, nausea, vomiting, right upper quadrant pain or tenderness, fever, rash, and/or eosinophilia (>5%)
  - Grade 4 diarrhoea, hypothyroidism, hyperthyroidism, hypophysitis, adrenal insufficiency, rash, toxic epidermal necrolysis, Stevens-Johnson syndrome, diabetes, other immune-related adverse reaction, or creatinine elevation
  - Grade 3 myocarditis or pneumonitis
  - Solicited local adverse events: If three out of the first 20 participants dosed with a study vaccine, or >10% of participants, thereafter, are followed by the same Grade 3 solicited local adverse event

- Solicited systemic adverse events: If three out of the first 20 participants dosed with a study vaccine, or >10% of participants, thereafter, are followed by the same Grade 3 solicited systemic adverse event
- Unsolicited adverse events: If three participants of the first 20 participants dosed, or >10% of participants, thereafter, develop a Grade 3 unsolicited adverse event of the same type that is considered related to study vaccine

Other potential reasons for discontinuation of the second planned dose of nivolumab for Group 4 are found in [Appendix 2 – Toxicity Management Guidelines for Nivolumab](#).

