### 6.1 Screening and Baseline Assessments

Written informed consent for participation in the study must be obtained before performing any study specific screening tests or evaluations according to the process in [Section 13.4](#).

The following will be performed at screening:

- Demographic data will be collected
- Height and weight will be measured
- A medical and disease history will be recorded, including any medications being taken
- A blood sample will be taken for HIV, HCV, HBV (quantitative HBV DNA and quantitative HBsAg), HDV diagnostic testing
- A urinalysis dipstick test will be performed
- A urine drug screen will be performed
- A urine pregnancy test will be performed, childbearing status recorded and if of childbearing potential, assessment of contraceptive measures performed
- Blood samples will be taken for haematology (including prothrombin time [PT] and INR), biochemistry and liver function tests (LFTs)
- A full physical examination will be performed
- Vital signs (pulse rate, blood pressure and temperature) will be measured

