##### *7.1.4.1 Haematology*

A sample of venous blood will be collected according to the central laboratory procedures.

The following will be measured: full blood count, haemoglobin, haematocrit, erythrocytes, mean cell volume, mean corpuscular haemoglobin, mean corpuscular haemoglobin concentration, leukocytes, neutrophils, lymphocytes, monocytes, eosinophils, basophils, PT and platelets.

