#### 7.1.4.2 *Biochemistry*

A sample of venous blood will be collected according to the central laboratory procedures.

The following biochemistry parameters will be measured: sodium, potassium, urea nitrogen, creatinine and albumin and LFTs (alkaline phosphatase, gamma-glutamyl transpeptidase, ALT, AST and direct bilirubin).

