#### ***7.4.2 Laboratory Safety Tests***

Laboratory safety tests will be performed at each of the timepoints according to [Table 2](#), as per [Sections 7.1.4.1](#) and [7.1.4.2](#). Extra laboratory safety tests may be performed if the Investigator deems them to be necessary to fully evaluate an adverse event. In the event that the Investigator elects to order non-protocol-specified laboratory tests, the Investigator must record the rationale for the tests and a determination of clinical significance of the result in the source documents. The Investigator must keep the local Medical Monitor informed of adverse events of clinical significance.

Abnormal results and findings will be discussed as applicable with the participant, and the participant will be referred for follow-up with their healthcare provider if necessary.

Results from the LFTs obtained on the study must be reviewed by the Investigator (or a designee who is a medically qualified study team member) and managed in accordance with the study centre procedures. The clinical significance of all results outside of the normal range will be determined by the Investigator and may be reported as an adverse event at the discretion of the Investigator.

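### The group liver hold in Protocol 3.1.3 tests total bilirubin, but the scheduled post-dose panel names direct bilirubin only

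*Protocol*

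**What the plan says.** **The hold.** Protocol 3.1.3 sends the data to the DMC when the investigator sees a reasonable possibility that the vaccine caused a listed event "in one or more participants at any dose. Vaccinations will be put on hold pending this review". One listed event is ALT or AST above 3 x ULN "and total bilirubin >2 x ULN or International Normalised Ratio (INR) >1.5". A second liver criterion pairs the same transaminase threshold with symptoms or eosinophilia and needs neither bilirubin nor INR.

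**Bilirubin.** Section 7.1.4.2 defines the panel as "LFTs (alkaline phosphatase, gamma-glutamyl transpeptidase, ALT, AST and direct bilirubin". The synopsis agrees on the analyte and gives the timing: "ALT, AST and direct bilirubin) will be analysed at screening, pre-vaccination on Days 0 and 28, on Days 7 and 35", then Months 3, 6 and 9. Section 7.4.2 applies the 7.1.4.1 and 7.1.4.2 panels at the Table 2 visits. Its provision for more testing is discretionary: "Extra laboratory safety tests may be performed if the Investigator deems them to be necessary to fully evaluate an adverse event".

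**INR.** The synopsis lists "fibrinogen, prothrombin time and INR, and platelets) will be analysed at screening" and at every later draw. The body names INR at screening only: "Blood samples will be taken for haematology (including prothrombin time [PT] and INR), biochemistry and liver function tests (LFTs" (6.1). The haematology panel in 7.1.4.1 ends "leukocytes, neutrophils, lymphocytes, monocytes, eosinophils, basophils, PT and platelets", so it has prothrombin time (PT) but not INR.

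**SAP.** Table 6 lists bilirubin, direct bilirubin, INR and PT without a collection schedule. Section 12.7.2.3 grades the direct fraction as the bilirubin increase.

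**The concern.** Direct and total bilirubin are different analytes with different upper limits, so a threshold on total bilirubin cannot be read from a direct result. The choice of direct bilirubin looks deliberate. The Version 4.0 summary of changes says that direct and not total is measured, and exclusion criterion 6 uses direct. The hold was not brought into line, and neither were the immune-related hepatitis rows of Appendix 2, which also refer to total bilirubin. (Those rows are cited for the analyte only: Group 4 is closed and Group 3 receives a single nivolumab dose.)

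Liver injury is a central risk in this trial. Section 3.2 restricts eligibility to limit vaccine-driven liver toxicity, section 8.3 makes hepatitis flares events of special interest, and section 3.3 names hepatitis as a nivolumab risk. A hold written to act on one participant should rest on a measurement that the schedule provides.

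**Working it through.** **1. Count the draws.** Table 2 schedules liver function tests after the first dose on Day 7, Day 28 (pre-dose), Day 35 and Months 3, 6 and 9, which makes 6. The optional UK visit 7 days after a Month 3 boost is left out; the SAP change history says no participant had that boost.

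| Analyte | Named at post-dose draws | Source |
|---|---|---|
| Total bilirubin | 0 of 6 | synopsis; 7.1.4.2 |
| Direct bilirubin | 6 of 6 | synopsis; 7.1.4.2 with 7.4.2 |
| INR | 6 of 6 | synopsis |
| INR | 0 of 6 | body (6.1, 7.1.4.1) |
| PT | 6 of 6 | 7.1.4.1 with 7.4.2 |

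The section 6 visit lists themselves name PT after dosing only at Month 9 (6.3.4), so PT timing also needs tidying.

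**2. See what other rules catch.** With raised liver tests, Appendix 1 grades bilirubin as Grade 3 at 1.51 to 1.75 x ULN and Grade 4 above that. PT is Grade 3 at 1.21 to 1.25 x ULN and Grade 4 above. ALT and AST are Grade 3 at 5.1 to 10 x ULN and Grade 4 above. A Grade 4 value may be held as life-threatening. The SMC reviews ALT or AST above 10 x ULN, or above 5 x ULN for more than 3 weeks (8.1.4). Two cases are left.

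*Case A, no numerical rule fires.* The participant has no symptoms or eosinophilia. ALT or AST is above 3 and up to 5 x ULN, total bilirubin is above 2 x ULN, and direct bilirubin and PT are below Grade 3 (direct at most 1.5 x ULN, PT at most 1.20 x ULN). Let r be the ULN for direct bilirubin divided by the ULN for total. Then

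direct/total < (1.5 x ULN direct) / (2 x ULN total) = 0.75r.

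The documents give no ULNs. Assuming r between 0.2 and 0.4, the direct fraction must be below 0.75 x 0.2 = 15% to 0.75 x 0.4 = 30%.

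*Case B, only the individual rule fires.* At least one value is Grade 3 and none is Grade 4, again with total bilirubin above 2 x ULN and no symptoms or eosinophilia. Section 3.1.4 withdraws that participant if the event is related and stays at Grade 3 for more than 72 hours. It does not hold the group. Direct bilirubin can be at most 1.75 x ULN, so

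direct/total < 1.75r/2 = 0.875r,

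which is 17.5% to 35% on the same assumed r. PT must be at most 1.25 x ULN. Case B is thus only a little wider than case A in bilirubin terms, although it takes in ALT or AST up to 10 x ULN.

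**3. Compare the group triggers in case B.** The liver hold needs 1 participant. The rule for related Grade 3 unsolicited events of one type needs 3 of the first 20, then more than 10%. The denominator after the first 20 is not clear, so both readings are shown for the planned 52:

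- Over the 52 - 20 = 32 later participants: 3/32 = 9.4% and 4/32 = 12.5%, so at least 4.
- Over all 52: 5/52 = 9.6% and 6/52 = 11.5%, so at least 6.

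These are trigger levels. They do not estimate how often the gap would matter.

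**The case against.** The best defence accepts the mismatch and disputes its consequence.

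- **Other routes exist.** Hepatitis flares are reported as for SAEs (8.3). A related, medically important event can be an SAE and so hold vaccination on one participant. The investigator must review liver results and may pause vaccination in the whole study (7.4.2, 8.1.1). The DMC can place the study on hold (8.1.5). All of this is true and makes harm less likely. But these are reporting duties or judgements, and they do not replace a stated numerical trigger. The hold also needs a causality judgement, but that judgement comes after the laboratory criterion has been seen to be met.
- **The SAP suggests the data exist.** Table 6 lists bilirubin beside direct bilirubin, and the change history says the list was updated from data received. Some total bilirubin results may well have been reported, and laboratory procedures outside these documents might explain them. Table 6 also lists the FibroTest score, which the protocol names only at screening, so a listing there does not show post-dose collection. What stands is a limit on the claim: it concerns what the protocol schedules, not what the laboratory in fact reported.
- **Both cases are narrow.** This stands, as the direct-fraction bounds show for A and B alike.
- **INR is not a functional gap.** This stands too. It is an inconsistency between synopsis and body.
- **The hold could be restated in direct bilirubin.** That is possible without a new test, but it needs a justified threshold, and the documents supply none for this purpose.

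**Conclusion.** The concern holds. As written, the total-bilirubin limb of a one-participant safety hold is not supported by any of the 6 scheduled post-dose draws, and no rule requires the missing test when transaminases rise. INR needs only alignment of the text.

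The practical gap is limited to predominantly indirect hyperbilirubinaemia, with a direct fraction below about 15% to 30% in case A or 17.5% to 35% in case B. Those ranges rest on an assumed r of 0.2 to 0.4. In case B the group trigger moves from 1 participant to 3 of the first 20, and later to at least 4 of 32 or 6 of 52. No missed-event rate can be derived. Confidence is high on the mismatch in the text. It should be fixed because the rule is a safety rule and the repair is small, not because many events are likely to be missed.

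**What to change.** - Add total bilirubin to 7.1.4.2 and INR to 7.1.4.1 at the Table 2 post-dose draws. Alternatively, require reflex total bilirubin and INR whenever ALT or AST exceeds 3 x ULN.
- Align the synopsis, 7.1.4.1 and the section 6 visit lists on PT and INR.
- As a clarification only, bracket the rule in 3.1.3: ALT or AST >3 x ULN AND (total bilirubin >2 x ULN OR INR >1.5).

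The cost is a small laboratory charge on blood already drawn, or only when the reflex threshold is met, plus wording in an amendment and the laboratory manual. No visits are added.

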### ***3.1.4 Individual Stopping Rules (All Vaccinated Study Participants)***

In addition to the above stated group holding rules, stopping rules for individual participants will apply (i.e. in addition to withdrawal of individuals from a second vaccination). Study participants who present with at least one of the following stopping rules will be withdrawn from further vaccination in the study:

- **Local reactions:** injection site ulceration, abscess or necrosis
- **Laboratory AEs:**
  - The participant develops a Grade 3 laboratory adverse event considered possibly, probably or definitely related within 7 days after vaccination and persisting continuously at Grade 3 for >72 hours
- **Systemic solicited adverse events:**
  - The participant develops a Grade 3 systemic solicited adverse event considered possibly, probably or definitely related within 2 days after vaccination (day of vaccination and one subsequent day) and persisting continuously at Grade 3 for >72 hours
- **Unsolicited adverse events:**
  - The participant has any Grade 3 adverse event considered possibly, probably or definitely related to vaccination, persisting continuously at Grade 3 for >72 hours
  - The participant has an SAE considered possibly, probably or definitely related to vaccination
  - The participant has an acute allergic reaction or anaphylactic shock following the administration of vaccine investigational product

If the participant has an acute illness (moderate or severe illness with or without fever) or a fever (oral temperature > 37.5°C) at the scheduled time of administration of investigational product, the participant will not receive the vaccine at that time. The vaccine may be administered to that participant at a later date within the time window specified in the protocol or the participant may be withdrawn from the study at the discretion of the Investigator.

All vaccinated participants will be followed for safety until resolution or stabilisation (if determined to be chronic sequelae) of their SAEs.

### 3.2 Discussion of Study Design, Including the Choice of Control Groups

This is a first in human study of the combination of ChAdOx1-HBV followed by MVA-HBV vaccines (VTP-300) and is designed to assess the safety and reactogenicity of these vaccines given with and without nivolumab in the target CHB population.

Standard clinical study safety assessments are used including adverse events, laboratory tests, vital signs and physical examinations. Foreseeable adverse events following vaccination are solicited from participants daily for the first 7 days post-vaccination using an electronic diary (eDiary; plus an assessment at the study centre on each vaccination day). Specific grading scales are defined for severity of solicited and unsolicited adverse events and abnormal laboratory results for participants in the lead-in phase (Section 8.2.4.1). Study stopping/holding criteria have been defined, with a DMC review mandated if one of these is met (Section 3.1.3).

The ChAdOx1-HBV dose is  $2.5 \times 10^{10}$  vp, based on the review of the two doses studied in HBV001 ( $2.5 \times 10^9$  vp and  $2.5 \times 10^{10}$  vp). Safety data from all healthy volunteers was reviewed from HBV001 by the SMC, and the higher dose was chosen to use in this study. To further minimise the risk that immune responses generated by vaccination do not result in liver toxicity, only those participants whose DNA levels are well controlled on antivirals will be included in the study, and those with advanced liver fibrosis or cirrhosis will be excluded. The safety of MVA-HBV will be evaluated by the SMC after the first 6 participants have received the first dose, to include at least 7 days safety data, prior to initiation of the prime-boost regimen of ChAdOx1 followed by MVA with and without nivolumab.

The present standard measure to assess the likelihood of functional cure is the level of circulating HBsAg, although the exact contributions of episomal cccDNA or integrated DNA are not entirely clear. Other measures under investigation to assess virologic effects include measurement of hepatitis B DNA and effect on hepatitis eAg seroconversion. Other measure of virologic activity under study and without full licensure include measurement of hepatitis B core-related antigen, and measurement of circulating hepatitis B full length pre-genomic RNA.

### **3.3 Benefit Risk Assessment**

There are potential known and unknown risks associated with vaccination. With any vaccine, including those that are licensed, there is a rare risk of anaphylaxis which can be fatal. Participants will therefore be observed in the clinic for at least 30 minutes post-vaccination and post-nivolumab infusion.

Intramuscular injection of vaccines frequently causes the local and systemic signs and symptoms that are being collected as adverse events. These will be solicited from the participant for the first 7 days after each vaccination to ensure they are not occurring more frequently or are more severe than expected based on previous experience with the same or similar viral vectors. After this time, unsolicited adverse events will be collected at each clinic visit throughout the study.

With any new treatment there is always a possibility of unexpected adverse events. Holding and stopping rules have been defined for the study (see [Section 3.1.3](#)) and the DMC will perform a review of safety data if one of these is met. There are also routinely scheduled reviews of safety during the lead-in phase by the SMC. Further detail is provided in the Investigator's Brochure.

The ChAdOx1 and MVA vectors have been widely administered for many pathologies without significant safety concerns (see [Section 1.4](#)). Further detail is provided in the Investigator's Brochure.

As this is an early development study with little clinical data, there may be no benefit to study participants. The participants will however receive additional monitoring of their HBV status compared to the standard of care.

Nivolumab, at full dose, is associated with a variety of adverse effect, including potential death. Common adverse effects include thyroiditis, colitis, pneumonitis, hepatitis, myocarditis, and other adverse immune related effects. In the published data using nivolumab at 0.3 mg/kg the most common adverse events were fatigue, headache and cough, with no immune-related adverse events observed [35].

## 4 STUDY POPULATION

### 4.1 Number of Participants

It is planned that up to approximately 52 participants with CHB infection and virally suppressed with oral antiviral medication will be enrolled in the study. Chronic HBV participants will be recruited/deemed eligible by hepatologists, infectious disease specialists or physicians experienced in treating CHB participants. Centres not meeting the enrolment expectations will be considered for replacement with the addition of a new centre. If participants leave the study before all follow-up visits are completed (for any reason), they may be replaced at the discretion of the study team. A log of all participants enrolled into the study (i.e. having given informed consent) will be maintained in the Investigator's Site File (ISF) at the study centre irrespective of whether they have been treated with vaccine or not.

Version 6.0 of the protocol has closed Groups 1 and 4 to further randomisation following analysis of on-going data; Groups 2 and 3 will continue to recruit approximately 16 participants in a 1:1 ratio.

The number of participants is based on feasibility considerations rather than formal sample size calculations. A total of up to approximately 52 participants with CHB infection is considered sufficient to confirm the safety, tolerability and immunogenicity of ChAdOx1-HBV followed by MVA-HBV, ChAdOx1-HBV plus MVA vaccines with or without nivolumab, and to answer the objectives of the study.

The statistical considerations used to determine the number of participants planned and evaluable are presented in [Section 10.1](#).

